3.4. Treatments

[figure not shown]
3.4.1. Investigational Products and Control

Investigational Product(s):

CCP-020 (Diacerein 1%) Topical Ointment

CCP-020 is a topical ointment, 1% (w/w). All excipients used in the topical formulation meet United States Pharmacopeia (USP)/ National Formulary (NF) criteria and are commonly used in

ointment formulations. CCP-020 (Diacerein 1%) topical ointment is packaged in aluminum tubes, at 25 g/tube.

CCP-020 topical ointment and vehicle ointment will each be applied in an amount of 0.2 mL to 2 sites (2 cm x 2 cm) on the infrascapular area of the subjects' backs for 24 hours (± 4 hours) under occlusive patch conditions (Tapemark - WebrilTM). The patch will be secured on the edges with hypoallergenic tape (3M Micropore[®]). This will be repeated twice each week during the 3-week Induction Phase, once on Monday during rest week 4 as applicable and once at Challenge. One application site of each study product will be irradiated and the other will remain non-irradiated.

CCP-020 topical ointment and vehicle ointment should be stored at room temperature (15°C/59°F to 30°C/86°F). The PI will be responsible for the suitable storage of the IPs in compliance with the storage instructions and must restrict access to the investigative personnel only.

Lot numbers will be given in the clinical study report.

Manufacturer:

TWi Pharmaceuticals will be responsible for the manufacturing and filling into the primary package; aluminum tubes. TWi Pharmaceuticals will be responsible to package and distribute to TKL. CCP will be responsible for final release of the product. TKL will be responsible for labeling the product upon site delivery.

Control

An untreated irradiated non-occlusive (open) 2 cm x 2 cm site will serve as a control.

3.4.2. Description of Investigational Products

CCP-020 (Diacerein 1%) topical ointment and vehicle ointment will be supplied in aluminum tubes for the clinical study. CCP-020 (Diacerein 1%) topical ointment and vehicle ointment were manufactured and packaged in accordance with good manufacturing practice (GMP).

3.4.3. Description of Patch Conditions

Material evaluated under occlusive patch conditions is applied to a 2 cm x 2 cm Webril® pad attached to a non-porous, plastic film adhesive bandage (medical tape). The patch is secured with hypoallergenic tape (Micropore), as needed.

3.4.4. Packaging/Labeling

The study medication tube label will show at least the following:

- Protocol number
- Storage conditions
- Instructions for use
- Expiration date
- Sponsor information
- Investigational drug warning
- Space to enter lot number.

A full product description can be found in the Investigator's Brochure (IB).¹

All study IPs should be stored at room temperature (15°C/59°F to 30°C/86°F).

3.4.5. Assignment to Treatment

3.4.5.1. Randomization

Each subject who signs an informed consent form (ICF) will be assigned a screening number. If the subject meets all of the inclusion and none of the exclusion criteria, and successfully completes the screening procedures, they will be enrolled in the study. Upon enrollment, each subject will be assigned a unique subject number and receive a randomization code, indicating application placement of the study materials. Each subject in this study will serve as his or her own control. All subjects will receive the IPs and control products at adjacent application sites, i.e. study product placement on the left side of the back will be the same as on the right side of the back.

CCP-020 (Diacerein 1%) topical ointment and vehicle ointment will be assigned in a randomized sequence to the test sites. The same study material will be applied to the same test site throughout the study.

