3. INVESTIGATIONAL PLAN

3.1. Study Design

This will be a randomized, double-blind, single-center, vehicle-controlled, within-subject comparison study of the study products, CCP-020 (Diacerein 1%) topical ointment, vehicle ointment, and an untreated irradiated non-occluded (open) control site. A total of 4 application sites (2 cm x 2 cm each) will be marked on the subject's back and distributed so that 2 sites are on each side of the back. One side of the back will be designated for irradiation after approximately 24 hours (± 4 hours) of study product application and the other side will remain non-irradiated. An additional site will be marked on the "irradiated side" of the back. The site will receive no study product, but will be irradiated at Challenge to serve as an untreated irradiated non-occluded control.

A defined area (approximately 50 cm²) on the infrascapular region of each subject's back will be irradiated to determine the minimal erythema dose (MED) of ultraviolet (UV) light.

During the 3-week Induction Phase, 0.2 mL of each study product will be applied to 2 sites twice each week (Monday and Thursday) for approximately 24 hours (± 4 hours) under occlusive patch conditions (6 applications). After patch removal, all application sites will be evaluated and one application site of each study product will be irradiated with 2 times the subject's MED using the full Xenon lamp spectrum. The sites will be evaluated by a trained evaluator. All sites will be reevaluated post irradiation, at approximately 48 hours later when irradiated on Tuesdays and at approximately 72 hours later when irradiated on Fridays except when irradiated on the last Friday of the Induction Phase or if a subject is taking a missed visit during induction, the sites will not be evaluated. These procedures will be performed each week for 3 weeks of the Induction Phase. Dermal reactions at the application sites will be evaluated using a visual scale that rates the degree of erythema, edema, and other signs of cutaneous irritation (see [Table 3](#) and [Table 4](#)).

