4.2. Sample Size and Power Considerations

The sample size of 50 evaluable subjects conforms to industry and regulatory standards for determination of irritation/sensitization when topical application to skin is followed by light exposure.

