4.6. Safety Evaluation

4.6.1. Assessment of Responses

All assigned scores during Induction and Challenge will be summarized by frequency counts by time point and treatment. The incidence of reactions will be summarized by frequency counts for each treatment. The mean score by subject and treatment, including all scores assigned during Induction, will be analyzed using Fisher's least significant differences in the analysis of variance (ANOVA) with factors subject and treatment. All pairwise comparisons will be performed: CCP-020 (Diacerein 1%) topical ointment on both the irradiated and non-irradiated sides, and vehicle ointment on both the irradiated and non-irradiated sides.

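### The placement of the two products is randomized, but the Induction irritation ANOVA has no position term; adding one costs 1 of 147 residual degrees of freedom

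*Combined protocol and SAP*

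**What the plan says.** Section 3.1 has four application sites "marked on the subject's back and distributed so that 2 sites are on each side of the back", so there are two positions per side. Under section 3.4.5.1 each enrolled subject will "receive a randomization code, indicating application placement of the study materials", and "CCP-020 (Diacerein 1%) topical ointment and vehicle ointment will be assigned in a randomized sequence to the test sites". The same section mirrors the layout: "study product placement on the left side of the back will be the same as on the right side of the back". No ratio, blocking or balance of the two placements is stated.

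For the analysis, section 4.6.1 says that each subject's mean Induction score by treatment "will be analyzed using Fisher's least significant differences in the analysis of variance (ANOVA) with factors subject and treatment". The four treatment levels are "CCP-020 (Diacerein 1%) topical ointment on both the irradiated and non-irradiated sides, and vehicle ointment on both the irradiated and non-irradiated sides". The synopsis and section 4.1 name the same two factors, and the synopsis lists the product comparisons within each side among the planned pairs. Position appears in none of the three places.

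The number of subjects is supported by convention only: "The sample size of 50 evaluable subjects conforms to industry and regulatory standards" (section 4.2). No SD, alpha, power or position effect is given.

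**The concern.** The one thing that each subject's code randomizes is which position each product takes, and the model ignores it. Because placement is mirrored, a position effect common to both sides moves both same-side product differences of a subject in the same direction. Two consequences follow for CCP-020 versus vehicle:

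- The position effect is counted as residual variation, so the error variance is too large for the comparison being made.
- If more subjects have CCP-020 in one position than in the other, part of the position effect is carried into the product difference.

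Induction irritation is a named safety endpoint (synopsis, section 3.1), and this ANOVA is its only inferential analysis. Depending on the realized split, the test can be too liberal or too conservative. In an irritation study, being too conservative means lost sensitivity to a real product difference.

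**Working it through.** The plan has no figure to reproduce, since the 50 subjects are not derived from an SD, effect size or power. The check therefore asks what the stated model does when a position effect exists.

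**Inputs from the documents.** N = 50; four sites per subject; two positions, mirrored; factors subject and treatment (four levels). Residual df = (50 − 1) × (4 − 1) = 147, or 146 with a position term.

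**Assumptions, not in the documents.** Residual SD σ = 0.25 points; additive position effect d = 0.1, 0.2 or 0.3 points, equal on both sides; each contrast tested at two-sided 5% with the pooled residual and no preliminary F test; allocation by coin-flip, exactly 25:25, or a realized 30:20.

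**Estimate.** With n1 and n2 subjects in the two placements, the same-side CCP-020 minus vehicle difference has

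- shift given the split = d × (n1 − n2)/N. At 25:25 this is 0; at 30:20 it is 0.2d, so 0.04 points at d = 0.2 and 0.06 at d = 0.3;
- true variance = 2σ²/N for a fixed split, and 2σ²/N + d²/N under coin-flip, where the shift averages zero.

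With no position effect, SE = √(2 × 0.0625/50) = √0.0025 = 0.050. Under coin-flip, d = 0.2 gives √(0.0025 + 0.0008) = 0.057, and d = 0.3 gives √(0.0025 + 0.0018) = 0.066.

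**Error term without position.** Expected residual mean square = σ² + d² × 50/147 at 25:25, σ² + d² × 49/147 under coin-flip, and σ² + d² × 48/147 at 30:20. Two cases show why the direction differs:

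- 25:25, d = 0.2: 0.0625 + 0.0136 = 0.0761. The reported SE is √(2 × 0.0761/50) = 0.055 against a true 0.050, so the test is conservative.
- Coin-flip, d = 0.3: 0.0625 + 0.0300 = 0.0925. The reported SE is √(2 × 0.0925/50) = 0.061 against a true 0.066, so the test is liberal.

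**Simulated type I error, CCP-020 versus vehicle on one side.**

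| Allocation | d | Without position | With position |
|---|---|---|---|
| Coin-flip | 0.1 | about 5.2% | about 5% |
| Coin-flip | 0.2 | about 6.0% | about 5% |
| Coin-flip | 0.3 | about 6.7% | about 5% |
| 25:25 | 0.1 | about 4.5% | about 5% |
| 25:25 | 0.2 | about 3.1% | about 5% |
| 25:25 | 0.3 | about 1.6% | about 5% |
| 30:20 | 0.2 | about 9% | about 5% |
| 30:20 | 0.3 | about 12% | about 5% |

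With position in the model, the SE is about 0.050 in every row. Under coin-flip, a split of 30:20 or worse in either direction has probability 0.20 (Binomial(50, 0.5)).

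**Power.** In units of the residual SD, take an assumed true difference of 0.56 SD, which has about 79% power when there is no position effect. If the position effect is 1 SD, adding the term raises power from 0.70 to 0.80 at 25:25 and from 0.66 to 0.79 under coin-flip. If it is 0.25 SD, the gain is under 1 percentage point.

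**Irradiated versus non-irradiated, same product.** Both sites share a position, so d cancels from the estimate. Only the error term is inflated, which makes this comparison conservative.

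**The case against.** The best defence is that the effect sizes are assumed and large. With σ = 0.25, effects of 0.2 and 0.3 points are 0.8 and 1.2 residual SDs. The sites are 2 cm squares, described as adjacent and at least 1 cm apart (sections 3.1, 3.4.5.1 and 3.5.1), and nothing in the documents suggests that neighbouring sites differ by so much. This stands: the size is unknown, and at 0.1 points little is lost.

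Three stronger readings are tempting, and the documents do not support them:

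- *The product comparison is biased.* Placement is randomized, so the expected bias is zero, and at 25:25 there is none. A shift exists only given an uneven split.
- *False positives are inflated.* That holds under coin-flip or an uneven split, but at 25:25 the test is conservative. Section 3.4.5.1 does not say which method applies, so unrestricted allocation is an assumption.
- *The trial's main conclusion is at risk.* The ANOVA covers Induction scores only. Section 4.6.2 leaves photosensitization to the Investigator and rules out deciding it by statistical methods.

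It can also be said that a single position term is too simple. Section 3.3.3 lets a product move to a new site up to twice, and an effect that differs by side needs 2 df. Both points are fair but easily handled. Finally, section 3.4.5.2 refers to an SAP still to be finalized, and no separate SAP text is among the documents, so the term could still be added there.

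A balanced list alone does not answer the concern. It removes the shift but leaves position in the error term, and the tolerability analysis uses Induction completers (section 4.3), whose split need not match the list.

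**Conclusion.** The point holds as a free improvement of low severity. The Induction irritation ANOVA omits the factor that the trial randomizes. Any position effect then inflates the residual, and an uneven split shifts the same-side product contrast by d × (n1 − n2)/N.

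Under the stated assumptions and position effects of 0.2 to 0.3 points, the type I error of a nominal 5% test ranges from about 1.6% (balanced) to about 12% (30:20). With the position term it is about 5% in every case. The consequence depends on a position effect and an allocation method that the documents do not give, and it may be negligible. The case for the change is that it helps under each allocation examined and costs almost nothing, not that harm has been shown.

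**What to change.** In the Induction ANOVA (synopsis, sections 4.1 and 4.6.1, and the SAP when finalized), make the factors subject, treatment and position, with position fixed and coded as randomized. State that a relocated product is analysed under its randomized position. In section 3.4.5.1, state that the placement list is generated in balanced blocks.

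The cost is 1 of 147 residual df, or 2 if the position effect is allowed to differ by side. No additional subjects, visits or data are needed; the randomized placement is already in each subject's code.

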3.4.5.2. Blinding

CCP-020 (Diacerein 1%) topical ointment, vehicle ointment, and control will not be blinded to investigative personnel involved in the preparation/application and removal of treatments.

Investigative personnel who are involved in the preparation/application and removal of the treatments will be unblinded and will not perform the evaluation of skin responses. The subjects and the trained evaluator who will be evaluating skin responses will be blinded to IPs and the treatment allocation; however, because of the demarcations/skin coloration remaining on the skin following patch removal, complete blinding of the evaluators cannot be completely assured.

Investigative personnel who are blinded, including the Investigator and trained evaluator involved in the evaluation of responses, will remain blinded during the course of the study until Database Lock and finalization of the Statistical Analysis Plan (SAP).

In the event of an emergency, if possible, the Investigator or designee will contact the Sponsor with notification of the intent to unblind the treatment codes prior to the actual unblinding. If it is not possible to notify the Sponsor prior to the unblinding, the Investigator or designee will contact the Sponsor immediately following the unblinding procedure and follow with a written notification to document the exact manner in which the code was broken and the justification for the unblinding. The Investigator will communicate the treatment identification to only the investigative personnel who require the information to manage the emergency. Unblinding will happen on site at TKL.

3.4.6. Prior and Concomitant Therapy

All medications, including over the counter (OTC) drugs and vitamins, taken within 28 days prior to the start of the study will be recorded at Screening. Thereafter, a record of all medications taken during the course of the study will be made. Information regarding the total daily dose, route of administration, start and discontinuation dates, and indication are to be captured on the subject's CRF.

The following prohibitions will apply for the duration of the study:

- There will be no use of systemic/topical anti-inflammatory analgesics which in the opinion of the investigative personnel will interfere with the study results, including anti-inflammatory medications such as aspirin (81 mg aspirin will be allowed at the discretion of the Investigator), Aleve, Motrin, Advil, or Nuprin for 72 hours prior to and during the study (occasional use of acetaminophen will be permitted);
- Use of sunbeds or sunlamps or deliberate exposure of the test sites to natural sunlight or to other sources of UV light;
- Participation in any other clinical study;
- Soaking of test areas; and/or
- Application of any product to the test areas.

The use of or change in the dose of any and all concomitant medication, either prescription or OTC, during the study will be recorded. The reason for use or change of dose of a concomitant therapy may need to be reported as an AE. Therapies (medication and non-medication therapies)

not restricted by the protocol may be used. Non-prohibited chronic therapies being used at Baseline may be continued.

All topical or systemic medication listed in the exclusion criteria are prohibited during this study. See the IB for information about possible drug-drug interactions.¹

3.4.7. Treatment Compliance

All patches will be applied and removed by investigative personnel. Whereas bathing will be allowed (low tub bath/frontal showers), the patched areas are not to be soaked and are to be kept as dry as possible, per the instructions to be given to each subject. Subjects will be instructed to contact the Investigator before starting any medication, including OTC remedies. In the case of an emergency treatment, the Investigator must be informed as soon as possible. A trained, experienced evaluator will assess study compliance.

Records of patch applications and visit schedule compliance will be recorded on the subjects' CRFs.

3.5. Visit Schedule and Assessments

3.5.1. Study Procedures and Visit Schedule

Screening

At Screening, the subjects will receive any necessary written and verbal information, and the informed consent of each subject will be obtained. Demographic data (including Fitzpatrick skin type) will be recorded, a medical history will be taken, and previous and concomitant medications will be reviewed. Eligibility will be determined by review of the inclusion/exclusion criteria.

- Any written and verbal information
- Informed consent
- Demographics
- Previous/concomitant medication
- Review of inclusion and exclusion criteria
- Medical history (including lifestyle and habits)
- Evaluation of application site area

Table 1: Fitzpatrick Skin Types

I	Always burns easily, never tans
II	Always burns easily, tans minimally
III	Burns moderately, tans gradually
IV	Burns minimally, always tans well
V	Rarely burns, tans very well
VI	Never burns, deeply pigmented ^{3,4}

Day 1

On Day 1, all subjects will be questioned regarding the entry criteria and female subjects of childbearing potential will undergo a UPT. If the subject fulfills all the inclusion and none of the exclusion criteria, he/she will be allowed participation in the study. Upon enrollment, each subject will be assigned a unique subject number and receive a randomization code, indicating application placement of the study products.

A baseline evaluation of the patch sites will be performed immediately prior to application of the patches to ensure that no conditions, markings, or coloration of the skin will interfere with interpretation of the study results.

A total of 4 application sites (2 cm x 2 cm each) will be marked on each subject's back, placing 2 sites on opposite sides of the back. The distance between the patches will be no less than one centimeter. The numbering of the test sites will remain the same throughout the study. The sites will be marked with an indelible, surgical marker.

Minimal Erythema Dose (MED) Determination

On Day 1, subjects will have an area of skin on their back, approximately 50 cm², divided into 6 equal sites marked with a surgical marker. Each of the sites will be irradiated with full spectrum UV light, with each exposure differing from the next by a factor of 1.25 (ie, each irradiated site will be exposed to a 25% greater dose of UV irradiation than the previous site).²

The areas involved in MED determination will be different from the study product application sites. Evaluation of the exposed sites will be performed on Day 2.

Induction

The Induction Phase consists of a series of 4 patch applications of the study products and subsequent irradiation and evaluations of the patch test sites over a 3-week Induction Phase.

Under occluded conditions, 0.2 mL of each study product, CCP-020 (Diacerein 1%) topical ointment and vehicle ointment will be applied to two Webril® pads. The patches will be secured with nonporous plastic film adhesive bandage (Blenderm tape) and hypoallergenic paper tape (3M Micropore™), as needed. The patches will then be applied to their assigned sites on each side of the back for 24 hours (± 4 hours). This process will be repeated twice each week (Mondays and Thursdays) during the 3-week Induction Phase. The same study product will be applied to the same test site throughout the Induction Phase.

Application sites will be evaluated immediately prior to study product application.

After 24 hours (± 4 hours) of study product application (eg, Tuesday and Friday), all patches will be removed. The sites will be evaluated using the scoring system detailed in [Section 3.5.7.1](#). One side of the back will be assigned for irradiation and the other will remain non-irradiated, ie, only one application site of each study product will receive irradiation. On all Tuesdays and Fridays, the sites designated for irradiation will be irradiated with 2 times the subject's MED using the full Xenon lamp spectrum.

Adverse events and concomitant medications will be reviewed at each visit and recorded as applicable.

One application/irradiation session may be missed during the Induction Phase. It must be made-up during Week 4. An additional application of study product may be applied on the Monday of rest week 4 if the subject misses an irradiation session during the Induction Phase of the study. No evaluation will be required following the final irradiation during the challenge period.

Rest Period (Weeks 4 and 5)

During the Rest Period of approximately 10-17 days, subjects will not receive any application of study materials. An additional application of study product may be applied on the Monday of rest week 4 if the subject misses an irradiation session during the Induction Phase of the study.

Challenge (Week 6)

On Day 1 of the Challenge Phase, subjects who have completed the Induction Phase and the Rest Period will have study product applications to naive sites in the same manner as applied during the Induction. A baseline evaluation of the naïve sites will be performed immediately prior to application of the patches to ensure that no conditions, markings, or coloration of the skin will interfere with interpretation of the study results. As in the Induction Phase, 0.2 mL of CCP-020 (Diacerein 1%) topical ointment and vehicle ointment will each be applied to 2 naive sites for approximately 24 hours (± 4 hours) under occlusive patch conditions. The clinical staff will then remove the patches and a trained evaluator will evaluate the test sites. There will be a main evaluator for the study; a backup evaluator will also be assigned in the event that an emergency occurs and the main evaluator is unable to attend the study visit. The designated sites and an additional untreated control site will be irradiated with 6 J/cm^2 of UVA (320-400 nm) followed by 0.5 times the MED of UVA/UVB (full-spectrum) irradiation, obtained by using a filtered light

source (see [Section 3.5.4](#)). Each site will be evaluated again at approximately 24 hours (± 4 hours), 48 hours (± 4 hours), and 72 hours (± 4 hours) post irradiation.

Adverse events and concomitant medications will be reviewed at each visit and recorded as applicable. A UPT will be performed for female subjects of childbearing potential at the last study visit.

Rechallenge

A Rechallenge should be performed if a cutaneous response observed during the Challenge Phase indicates possible photosensitization or at the discretion of the Investigator. If it is determined by the Investigator that a Rechallenge should be performed, the Rechallenge patches will be applied as soon as Challenge reactions have resolved. Just as in the challenge procedure 0.2 mL of each study product CCP-020 (Diacerein 1%) topical ointment and vehicle ointment, will each be applied to 2 naïve sites for approximately 24 hours (± 4 hours) using appropriate patches to further discriminate a photosensitization reaction from an irritation reaction. A baseline evaluation of the naïve sites will be performed immediately prior to application of the patches to ensure that no conditions, markings, or coloration of the skin will interfere with interpretation of the study results. Approximately twenty-four (24) hours (± 4 hours) after study product application, the clinical staff will remove the patches and a trained evaluator will evaluate the test sites. One site of each product and an additional untreated control site will be irradiated with 6 J/cm² of UVA (320-400 nm) followed by 0.5 times the MED of UVB (290-320 nm) irradiation using a filtered light source. All sites (irradiated and non-irradiated) will be graded for dermal reactions at approximately 24 hours (± 4 hours), 48 hours (± 4 hours), and 72 hours (± 4 hours) following irradiation. Concomitant medications and AEs will also be reviewed.

End of Study

At the EOS, all patches will be removed as described above, and the final evaluations of the test sites will be made.

An EOS examination will be conducted and consist of the following:

- Concomitant medication
- AEs
- UPT in females of childbearing potential

Concomitant medications and AEs will be reviewed and recorded during the whole study. For a detailed listing of scheduled study time points refer to the Visit Schedule and Assessments ([Table 2](#)).

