Study Design:	During the 3-week Induction Phase, CCP-020 (Diacerein 1%) Topical Ointment and vehicle ointment, will each be applied 2 times per week (Monday and Thursday) to 2 sites on the infrascapular area of the back under fully occlusive patch conditions for approximately 24 hours (± 4 hours). Minimal erythema dose (MED) irradiation will also be performed for each subject on Day 1. After patch removal, all application sites will be evaluated and one application site of each study product will be irradiated with 2 times the subject's MED using the full Xenon lamp spectrum. All sites will be evaluated at approximately 48 hours later when irradiated on Tuesdays and 72 hours later when irradiated on Fridays. An additional application of study product may be applied on the Monday of rest week 4 if the subject misses an irradiation session during the induction phase of the study. At Challenge, CCP-020 (Diacerein 1%) Topical Ointment and vehicle ointment will each be applied once to 2 naive sites on the infrascapular area of the back under fully occlusive patch conditions for approximately 24 hours (± 4 hours). After patch removal, all application sites will be evaluated and one site of each test product will be irradiated with 6 J/cm^2 of Ultraviolet A (UVA) followed by 0.5 times the subject's MED of UVA/Ultraviolet B (UVB). An additional untreated site will also be irradiated at Challenge and will serve as an untreated control. Each site, including the untreated control site, will be evaluated again at approximately 24 hours (± 4 hours), 48 hours (± 4 hours), and 72 hours (± 4 hours) following irradiation. A Rechallenge will be performed if a cutaneous response observed during the Challenge Phase indicates possible photosensitization or at the discretion of the Investigator.
Planned Sample Size:	50 evaluable subjects
Study Population:	Healthy adult male and female volunteer subjects
Investigational Products:	CCP-020 (Diacerein 1%) Topical Ointment Vehicle Ointment
Control:	An untreated irradiated non-occlusive (open) control site.
Efficacy Evaluation Criteria:	Not applicable

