3.5.3. Definition of Minimal Erythema Dose

Minimal erythema dose (MED) is defined as the length (in time) of light exposure required to produce a minimal erythema reaction 16 - 24 hours after irradiation using a standardized filtered UV light source that emits UVB (290-320 nm) as part of its emission spectrum.²

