3.5.4. Light source

The light source will be a Xenon Arc Solar Simulator (150 W), with UV-reflecting dichroic mirror, UVC-blocking filter, and visible/infrared blocking filter to generate a continuous emission spectrum in the UVA and UVB range (290 to 400 nm).² An additional filter is added during irradiation of the application sites to block UVB radiation allowing only UVA irradiation of the sites. The output is measured daily prior to irradiation using a radiometer/photometer.

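### The only light instruction for Rechallenge gives half the MED as UVB, whereas Challenge and the MED itself use full-spectrum light; probably a drafting slip, but uncorrected

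*Combined protocol and SAP*

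**What the plan says.** At Challenge, Section 3.5.1 gives a first step of 6 J/cm² of UVA (320-400 nm) and then "0.5 times the MED of UVA/UVB (full-spectrum) irradiation", with a reference to Section 3.5.4 for the light source. The Synopsis also gives UVA/UVB for the second step.

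At Rechallenge, Section 3.5.1 keeps the 6 J/cm² UVA step but continues "followed by 0.5 times the MED of UVB (290-320 nm) irradiation using a filtered light source". It does not refer to Section 3.5.4.

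The MED is determined on Day 1 as follows: "Each of the sites will be irradiated with full spectrum UV light, with each exposure differing from the next by a factor of 1.25". Section 3.5.3 says that the MED "is defined as the length (in time) of light exposure required to produce a minimal erythema reaction", using a source "that emits UVB (290-320 nm) as part of its emission spectrum". Section 3.5.4 describes a xenon arc simulator with output from 290 to 400 nm and one extra filter: "An additional filter is added during irradiation of the application sites to block UVB radiation allowing only UVA irradiation of the sites".

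Section 3.5.1 gives Rechallenge the task of telling photosensitization from irritation. Section 4.6.2 lets it confirm the Challenge finding where needed. Under Section 3.5.7.1, it decides cases in which both the irradiated and the non-irradiated product sites react.

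**The concern.** A confirmatory test should repeat the exposure that raised the suspicion. Read literally, Rechallenge changes the waveband of the second step and scales it to an MED that is not measured for that waveband. If a Challenge reaction then failed to recur, the changed light would be one more possible explanation, alongside irritation or chance. Section 4.6.2 reports the incidence of photosensitization by frequency counts, with 50 evaluable subjects planned, so even a single unresolved Rechallenge case would show in the result. Site staff would also have to choose between disregarding the stated wavelength limits and improvising a filter and a dose.

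**Working it through.** No sample size, power or error-rate figure is involved, so the check is a comparison of the light specifications.

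| Use of light | Dose | Spectrum | Section |
|---|---|---|---|
| MED determination | graded series, factor 1.25 | full-spectrum UV | 3.5.1 |
| Induction | 2 × MED | full xenon spectrum | 3.1, 3.5.1 |
| Challenge, step 1 | 6 J/cm² | UVA, 320-400 nm | 3.5.1 |
| Challenge, step 2 | 0.5 × MED | UVA/UVB, full spectrum | Synopsis, 3.5.1 |
| Rechallenge, step 1 | 6 J/cm² | UVA, 320-400 nm | 3.5.1 |
| Rechallenge, step 2 | 0.5 × MED | UVB, 290-320 nm | 3.5.1 |

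1. **What differs.** Between Challenge and Rechallenge, the UVA step, the 0.5 multiplier, the irradiated sites and the reading times agree. Only the waveband of step 2 differs.

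2. **Whether the dose is defined.** The Rechallenge instruction can be read literally in two ways. One is half the full-spectrum exposure time with the UVA filtered out. That uses the measured MED but omits the UVA part of the Challenge step. The other is half of a UVB-only MED, which the plan never measures. Neither repeats the Challenge exposure.

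3. **Whether the equipment delivers it.** The lamp gives 290-400 nm, and the one extra filter removes UVB. The described outputs are therefore full spectrum or UVA alone. A UVB-only output is not described.

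4. **Whether other text corrects it.** The Synopsis and Sections 3.1, 3.5.7.1 and 4.6.2 mention Rechallenge but give no light specification for it. The comparison with the Challenge procedure in the Rechallenge text concerns product application, not irradiation. No reason for a change of spectrum is given.

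5. **How much it touches.** For each rechallenged subject there are 2 products × 2 sites + 1 untreated site = 5 sites, of which 1 + 1 + 1 = 3 are irradiated. With readings at 24, 48 and 72 hours there are 5 × 3 = 15 post-irradiation readings, 3 × 3 = 9 of them at irradiated sites. These counts show how far the instruction reaches. They do not measure a dose error or a misclassification rate.

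6. **Secondary point: the untreated site.** Section 3.1 has it irradiated at Challenge, which means 0 times in Induction. Section 3.5.7.1, covering both Induction and Challenge, includes it in the irradiation. Read literally, that is 2 sessions per week × 3 weeks = 6 Induction exposures. Table 2 footnote d also says that this site is irradiated, and it appears against the Induction Fridays. If it belongs there, it could mean 1 exposure (the last Friday) or 3 (days 5, 12 and 19). The placement of that footnote is uncertain in the extracted table.

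**The case against.** The strongest reply is that the light would probably not change in practice. With the equipment described, any second step that contains UVB must be full spectrum, as at Challenge. Section 3.5.3 attaches the same 290-320 nm label to the source used for the MED, so the Rechallenge phrase may be loose shorthand for the ordinary MED. This makes a drafting slip the likelier explanation. It does not make the instruction right, because explicit wavelength limits in the only operating text invite literal use, and nothing else overrides them.

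The second reply also stands: the one-grade rule in Section 3.5.7.1 compares irradiated with non-irradiated sites within Rechallenge, and all irradiated sites there share the same light. The wording does not break that comparison.

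A reader might infer that Rechallenge will miss true photosensitization and bias the incidence downward. The documents do not support this. They give no spectral split for the lamp, no action spectrum for the product and no expected number of rechallenges, and the UVA step is unchanged. Under Section 4.6.2 the diagnosis also rests on the Investigator's judgement of the Challenge findings, with Rechallenge used only where necessary.

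**Conclusion.** The inconsistency is real and certain as a matter of text. As written, step 2 of Rechallenge has no matching dose reference, relies on a filter that is not described, and does not repeat the Challenge stimulus. It should be corrected because Rechallenge is the confirmatory procedure for the study's main safety question and the correction is trivial.

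The consequence is limited. It arises only for rechallenged subjects, who may be none, and only if staff follow the wavelength limits literally. That would need a UVB-isolating filter which the documents do not mention. The difference in dose cannot be quantified from the documents. The conclusion assumes that Rechallenge was meant to repeat Challenge; its shared UVA step, multiplier, sites and reading times suggest this, but the plan does not say it of the light.

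The timing of the untreated site's irradiation is a separate and lesser consistency matter.

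**What to change.** In the Rechallenge paragraph of Section 3.5.1, replace the UVB wording with the Challenge wording, "0.5 times the MED of UVA/UVB (full-spectrum) irradiation", and add the reference to Section 3.5.4. If a UVB-only step was in fact intended, the plan would instead need to specify the filter, a matching MED determination and the reason for the change.

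In the same edit, state in Section 3.5.7.1 that the untreated site is irradiated only at Challenge and Rechallenge. Check the sentence on the untreated site in Table 2 footnote d, and correct it or move it to the Challenge column.

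The cost is one line in Section 3.5.1, one clause in Section 3.5.7.1 and one footnote, with no added subjects, visits or procedures. Only the UVB-only alternative would add work, because it needs a further MED measurement.
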